4.1 Main outcome

Successful decanulation is defined as maintenance of spontaneous ventilation in the absence of recanulation, acute use of non-invasive ventilation (NIV) or death within 48 hours.

Factors potentially associated with successful decanulation will be collected prospectively:

- Severity factors related to the ICU stay:

o Total number of oro-tracheal intubations ;

o Number of days on mechanical ventilation;

o Curarisation or not with duration

o Whether or not prone sessions were performed with duration;

o Whether or not ECMO was used as a back-up;

o Number of pneumopathies acquired under mechanical ventilation;

o IGS2 ;

- Ventilatory factors :

o Number of failed extubations before tracheostomy in the ICU;

o Duration of mechanical ventilation before tracheostomy in the ICU (days);

o Type of tracheostomy used: percutaneous or surgical;

o Time to first attempt at Difficult-to-Wean Unit de-ventilation (days);

o Time to 24-hour at Difficult-to-Wean Unit de-ventilation (days);

o Time from 24-hour deventilation to successful DIFFICULT-TO-WEAN UNIT decanulation (days);

o Number of ventilator-associated lung diseases (VAPs) in at Difficult-to-Wean Unit;

- Respiratory factors:

o Ultrasound lung ventilation score on admission to at Difficult-to-Wean Unit;

o Diaphragmatic dysfunction on admission to at Difficult-to-Wean Unit;

o Bronchial fibroscopy abnormalities prior to decanulation;

- Extra-respiratory factors:

o Confusional state on admission to at Difficult-to-Wean Unit (CAM-ICU, Appendix 1);

o Existing swallowing disorders (assessed after 6 hours of ventilation) by the modified Cowling swallowing score (18);

o Oral status on admission to at Difficult-to-Wean Unit (normal, moderately impaired, dilapidated, no teeth);

o ICU-Acquired muscle weakness (MRC score) on admission to at Difficult-to-Wean Unit;

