5.1 Inclusion criteria

- Admission to DIFFICULT-TO-WEAN UNIT at Forcilles Hospital;
- Presence of a tracheotomy on admission to Difficult-to-Wean Unit;

- Presence of invasive ventilation on admission to Difficult-to-Wean Unit with a predicted duration of > 48 hours;

- Patient aged at least 18 years at the time of inclusion;
- Affiliation to or beneficiary of a social security scheme;
- Oral, free, informed and express consent of the patient or a relative.

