7.5 Assessment of swallowing disorders

As part of the patient's speech and language therapy, an assessment of swallowing disorders is carried out by a member of the speech and language therapy team when the patient tolerates several hours of deventilation per day.

For this purpose, we will use the modified Cowling swallowing score which consists of 4 points (Appendix 3): no disorder, abnormality to solids, abnormality to liquids, abnormality to liquids and solids.

The assessment is based on the detection of liquid, solid or liquid and solid false routes by ingestion techniques of coloured or uncoloured liquids/foods with the search for these potential false routes in the airways via tracheal aspirations through tracheostomy.

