7.7 Decanulation decision

The decision to decanulate follows a progressive de-ventilation and assessment protocol based on respiratory and extra-respiratory criteria:

Respiratory criteria :

- Patient under mechanical ventilation 24 hours a day: the tracheostomy cannula is a nonwindowed or a windowed cannula with a low pressure cuff of the Silhey® LPC, Bivona® Mid-Range Air Cuf or Portex® Blue-Line Ultra type; allowing to limit the risks of tracheal lesions due to the cuff;

- Patient under mechanical ventilation <18h/24h or dislocated > 6h/24h (with the cuff of the tracheostomy cannula deflated): the cannula is changed for a non fenestrated high pressure cuffed cannula such as Bivona® TTS. This type of cannula is with a plated silicone cuff and is very well tolerated and facilitates speech therapy exercises. The size of the tracheostomy cannula is sometimes reduced to facilitate the exercises but this is not consensual and is more a matter of practice specific to each department.

- Patient discharged during the day: generally 8am-6pm, then progressive lengthening of the time before nocturnal reventilation (plateau at 8pm-10pm-00am).

- Patients discharged during the day and early evening: this discharging is continued throughout the night. Complete 24-hour de-ventilation is recorded when the patient is de-ventilated for 48 hours without the need for re-ventilation.

- Patient is deventilated 24 hours a day: the next step consists of placing a plug over the tracheostomy orifice. Thus, the patient's "classical" respiratory tract is used and the patient is in a respiratory situation equivalent to a patient without a tracheostomy tube.

Extra-respiratory criteria:

After 48 hours with the cannula plugged, in the absence of a respiratory event, the patient is considered decanulable. Various assessments are carried out to ensure that there are no potentially negative predictive factors:

- Speech therapy: pharyngolaryngeal oedema is assessed by phonation exercises. These exercises can also be used to assess vocal cord and/or glossal damage. Swallowing of liquids and solids is tested.

- Physiotherapy: neuromuscular and diaphragmatic function (MRC score, ultrasound) are assessed.

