9.2.2 Data collection at inclusion

At the inclusion visit, the following data will be collected from the patient's computerised medical record, or directly from the patient or relative if data is missing:

- Age, sex (male/female), weight, height, body mass index (BMI);

Medical history: chronic heart disease (hypertension, coronary artery disease, dyslipidaemia, rhythm disorder), diabetes, chronic respiratory disease (Chronic Obstructive Pulmonary Disease (COPD), Sleep Apnoea Hypopnoea Syndrome (SAHOS), neurological disease, cancer, chronic renal failure, smoking (active, weaned, no), chronic alcoholism (yes, no);
 Data related to the initial ICU stay:

o Type of intensive care unit (medical, surgical, polyvalent) and type of institution (public, private non-profit, private);

o Reason for admission to intensive care: acute respiratory failure (ARF), ARF on chronic respiratory failure (CRF), cardiogenic shock, septic shock, haemorrhagic shock, polytrauma, post-operative, cardiorespiratory arrest (CRA), stroke, burns, pancreatitis, coma;

o IGS2 score on initial admission to the ICU.

- Number of failed extubations;
- Total duration of oro-tracheal intubation before tracheostomy (days);
- Number of VAPs (days);
- Performance of prone sessions (yes/no);
- If applicable, total duration of prone position (days);
- Use of ECMO support (veno-venous/arteriovenous/no);
- Tracheostomy performed (percutaneous/surgical/not);
- Resuscitation neuromyopathy (yes/no);

- Presence of BMR/BHR (yes/no);

- Limitation and discontinuation of active therapies (LATA) in the ICU (yes/no);

- Length of stay in intensive care (days);

- Type of tracheostomy cannula: uncuffed fenestrated, cuffed fenestrated, uncuffed non fenestrated;

- Cannula model (Shiley/Bivona/Trachoe/Other);

- Presence of mechanical ventilation (yes/no) and parameters:

o Mode: Controlled/PS/Other

o PS, PEEP, Vt, HR

o FiO2 (%)

- Biological check-up on admission within 48 hours of admission to DIFFICULT-TO-WEAN UNIT: haemoglobin, leucocytes, lymphocytes, neutrophils, troponin, renal function (urea, creatinine, GFR), metabolic function (calcium, magnesium, phosphate, TSH, cortisol at 8 hours, 25(OH)D) and inflammatory function (albumin, CRP);

- MRC score;

- Pulmonary ultrasound ;

- Diaphragmatic ultrasound;
- Confusional state by CAM-ICU (yes/no) (Appendix);
- Oral status (normal/moderate impairment/decay/no teeth);
- Vocal status (normal/minimal alteration/severe alteration/absence);

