- Swallowing disorders by modified Cowling score (liquids/solids/both/not);
- Presence of undernutrition (severe/moderate/minimal/no);
- Presence of a nasogastric tube (yes/no);
- Presence of a percutaneous gastrostomy (yes/no);
- Oral feeding resumed (yes/no).

For data collection regarding the ICU hospitalisation prior to DIFFICULT-TO-WEAN UNIT hospitalisation, this will be done on the basis of hospitalisation reports and, if necessary, by requesting additional information through telephone calls to the ICU services or the attending physician.

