9.5 Summary of all visits

| Données/actes | Pré- inclusion | Inclusion | Fin de recherche | | |
|--|-------------------|-----------|------------------|--|--|
| Recueil dans le CRH en réanimation, le DMI ou auprès du patient/proche | | | | | |
| Information du patient ou du | х | | | | |
| proche | Х | | | | |
| Consentement du patient ou du | | x | | | |
| proche | | ~ | | | |
| Données anthropométriques | | x | | | |
| (âge, poids, taille, sexe, IMC) | | | | | |
| Antécédents médicaux | | X | | | |
| Données liées au séjour initial en | | X | | | |
| réanimation | | | | | |
| Données liées à la ventilation : | | N N | | | |
| trachéotomie, VM (modes et | | X | | | |
| paramètres) | | | | | |
| Etapes sevrage ventilatoire | | | | | |
| (temps avant déventilation | | | X | | |
| journée, temps avant | | | | | |
| déventilation complète) Durée de séjour en SRPR | | | V | | |
| Modalités de sortie du SRPR | | | X X | | |
| | | | ^ | | |
| Mesures cliniques, physiologiqu | ies et biologiq | ues | | | |
| Bilan biologique (urée, créatinine, | | | | | |
| DFG, troponine, Hb, leucocytes, | | X | | | |
| PNN, lymphocytes, calcium, | | | | | |
| magnesium, phosphates | | | | | |
| Albumine, pré-albumine, CRP, | | X | | | |
| 25(OH)D, TSH, cortisol à 8h | | | | | |
| Scores fonctionnels | | | | | |
| MRC | | X | X | | |
| Hand-grip | | X | Х | | |
| Calorimétrie | | X | | | |
| Impédancemétrie :masse | | x | | | |
| maigre, masse grasse, dilution | | ^ | | | |
| Echographie | | | | | |
| Diaphragme | | X | X | | |
| Pulmonaire | | X | Х | | |
| Nutrition | | | | | |
| Alimentation PO, entérale par | | | V | | |
| GEP ou SNG | | X | X | | |
| Orthophonie | | I | | | |
| Troubles déglutition, état bucco | | v | | | |
| dentaire, voix, état confusionnel | | X | | | |

10 Statistics

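### The swallowing score is collected at inclusion only, but section 7.5 makes it depend on daily de-ventilation, so for patients still fully ventilated at inclusion it is unavailable or conditional on weaning progress

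*Combined protocol and SAP*

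**What the plan says.** The score appears in the list of candidate factors in section 4.1 as "Existing swallowing disorders (assessed after 6 hours of ventilation) by the modified Cowling swallowing score". The other three extra-respiratory factors there (confusion, oral status, MRC score) are each tied to admission; this one is not.

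Section 7.5, on usual care, has the speech therapy team assess swallowing "when the patient tolerates several hours of deventilation per day".

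Section 9.2.2 opens with "At the inclusion visit, the following data will be collected from the patient's computerised medical record", and its list includes "Swallowing disorders by modified Cowling score (liquids/solids/both/not". The schedule in section 9.5 has a row beginning "Troubles déglutition, état bucco", marked under inclusion and under no other visit. The end-of-research list in section 9.3 contains no swallowing score.

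On the patients' state at entry, section 5.1 requires "Presence of invasive ventilation on admission to Difficult-to-Wean Unit with a predicted duration of > 48 hours". Section 9.1.2 says that some are sedated on admission. Section 4.1 treats coming off the ventilator as an event timed within the unit stay: "Time to first attempt at Difficult-to-Wean Unit de-ventilation (days".

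Section 7.7 adds a swallowing check before decanulation, after 48 hours with the cannula plugged ("Swallowing of liquids and solids is tested"), but names no score for it. Section 10 gives no rule for missing values.

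**The concern.** A patient who is ventilated around the clock at inclusion cannot satisfy both section 7.5 and sections 9.2.2 and 9.5. Either the field is empty at the only scheduled collection point, or it is filled in later, on a day set by how fast that patient weans. In both cases, having a score, and when it was taken, depends on progress towards the outcome being modelled.

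Two gaps make this matter for the analysis. The response options in 9.2.2 cover liquids, solids, both or none, so a patient who was never tested is not distinguished from one who was tested and found normal. Section 10 does not say what happens to a patient without a value. Ordinary logistic regression drops such a patient. If the field were instead filled with the option for no disorder, the least-weaned patients would be counted as having normal swallowing. That would weaken or reverse the apparent link between swallowing disorder and failure.

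The same factors are reused in section 4.2 for weaning from invasive ventilation. There the dependence is more direct, because under 7.5 the score itself requires progress towards that outcome.

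**Working it through.** **Timing statements side by side**

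| Section | When the score is taken | Possible at inclusion for a fully ventilated patient? |
|---|---|---|
| 4.1, read literally | after 6 hours on the ventilator | yes |
| 4.1, if a slip for de-ventilation | after 6 hours off the ventilator | no |
| 7.5 | once several hours off per day are tolerated | no |
| 9.2.2, 9.5 | inclusion visit only | required then |

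A slip in 4.1 is plausible, because section 7.7 has a step at more than 6 hours in 24 off the ventilator. On that reading 4.1 agrees with 7.5 and conflicts with 9.2.2 and 9.5. Read literally, 4.1 fits the inclusion visit and conflicts with 7.5. Either way two time points remain, and they cannot both hold for a patient who is fully ventilated at inclusion.

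**The plan's own figure**

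Inputs from section 10.1: 6 variables, 10 events per variable, 60% success.

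N = 6 × 10 / 0.60 = 100, which reproduces the stated sample size. Expected successes are 100 × 0.60 = 60, and expected non-successes 100 − 60 = 40.

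**Illustration A: missingness tied to the outcome**

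The documents give no missing rate, so the fraction f of non-successes never scored is an assumption. The illustration also assumes that patients who are never decanulated count as failures and that all successes are scored.

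Failures left = 40 × (1 − f). Apparent success = 60 / (60 + failures left).

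| f (assumed) | Failures left | Complete cases | Apparent success |
|---|---|---|---|
| 0% | 40 | 100 | 60% |
| 25% | 30 | 90 | 60/90 = 67% |
| 50% | 20 | 80 | 60/80 = 75% |
| 75% | 10 | 70 | 60/70 = 86% |

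**Illustration B: missingness unrelated to the outcome**

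If 10%, 20% or 30% of all patients had no score regardless of outcome, successes would be 60 × 0.9 = 54, 60 × 0.8 = 48 or 60 × 0.7 = 42. That is 9, 8 or 7 per variable for 6 variables, against the planned 10. Here the success rate stays at 60% and only precision is lost.

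**When the score affects the model**

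Section 10.3 screens each variable at p < 0.20 and then selects by AIC. The score is one of 21 candidates listed in 4.1 (7 severity, 7 ventilatory, 3 respiratory, 4 extra-respiratory). Its own univariate comparison always uses scored patients only. It restricts the multivariable set only if it passes the screen. In that case AIC comparisons need the same rows throughout, so unscored patients are absent from every model compared with it.

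**The case against.** Four points on the other side carry weight.

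*Some patients may be testable at inclusion.* Section 5.1 requires invasive ventilation but not 24 hours a day. The inclusion items in 9.2.2 cover vocal status, uncuffed cannulas and resumed oral feeding, which leaves room for patients who arrive already off the ventilator part of the day. A reader might infer that no patient can be scored at inclusion; the documents do not support that. The conflict concerns those still fully ventilated, and their number is not given.

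*The data form is not in the documents.* A reader might infer that it has no code for an untested patient, or that such patients will be entered as having no disorder. Only the categories in the protocol text are visible, and nothing says how a blank would be handled. What stands is that the protocol does not make the distinction and has no missing-data rule.

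*The outcome-driven missingness depends on who counts as a failure.* Sections 4.1 and 10.3 do not say that never-decanulated patients do. If only decanulated patients were compared, all would have passed the steps in 7.7, including a swallowing test, and missingness tied to the outcome would largely disappear. The variable timing of the score would remain. The wider reading is nevertheless suggested by section 10.1, which applies 60% to all 100 patients; by 4.2, which takes all included patients as denominator; and by the 2 to 25% decanulation failure rate in section 1, well below the implied 40%.

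*Excluding the score as an admission predictor would prejudge the timing.* This is right: such an exclusion follows only if the sponsor keeps the de-ventilation condition.

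**Conclusion.** The conflict is real and lies between two time points: inclusion only (9.2.2, 9.5) and after several hours of daily de-ventilation (7.5). A reader might count three incompatible timings because there are three wordings, but 4.1 agrees with one side or the other on either reading.

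For patients still fully ventilated at inclusion, this candidate factor is unavailable or conditional on weaning progress. If it enters the model, unscored patients drop out or risk being counted as free of disorder.

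The size cannot be fixed from the documents. The rise in apparent success from 60% to 67%, 75% or 86% rests on assumed rates of 25%, 50% or 75% unscored among 40 expected failures, and on counting never-decanulated patients as failures. It shows how far the analysed set could shift; it is not a forecast. The point goes beyond missing detail because it determines who is analysed.

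**What to change.** 1. Reconcile 4.1, 7.5, 9.2.2 and 9.5 to one defined time point for the score. Which one is for the sponsor to decide.
2. Record the date of the assessment and the hours off the ventilator that day.
3. Add a category for not tested or stage not reached, distinct from no disorder.
4. State in section 10 that patients without a score are not dropped from the main model because of it, and say how this is done.
5. If the sponsor keeps the score conditional on de-ventilation, do not treat it as an admission predictor. Report it in a secondary analysis of assessed patients, labelled as conditional on reaching that stage. That analysis remains selected on weaning progress and does not recover the unscored failures; the label makes this explicit.

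The cost is protocol wording and a few data fields, with no added procedure. If item 5 applies, the estimate for this one factor becomes conditional and less precise.

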4.2 Secondary outcomes

- Proportion of successful decanulation among all included patients (prevalence of successful decanulation);

- Proportion of successful weaning from IV among all included patients (prevalence of successful weaning from IV). Successful weaning from invasive ventilation is defined as the absence of invasive ventilation >48h ;

- The same factors potentially associated with successful weaning from IV will be collected as described in section 4.1.

- Collection of biological parameters within the first 48 hours of admission to Difficult-to-Wean Unit: haemoglobin, leukocytes, lymphocytes, neutrophils, troponin, renal function (urea, creatinine, GFR), metabolic function (calcium, magnesium, phosphate, TSH, cortisol at 8 hours, 25(OH)D) and inflammatory function (albumin, CRP);

- Ventilatory parameters on admission to Difficult-to-Wean Unit: ventilatory mode (VAC, VSAI), ventilatory settings (FiO2, PEP, AI, FR, Vt);

- Demographic characteristics of these patients during Difficult-to-Wean Unit hospitalisation: mortality, length of hospitalisation, duration of invasive ventilation.

- Nutritional assessment by evaluation of grip strength by Handgrip at admission and discharge from the Difficult-to-Wean Unit, by evaluation of the stage of sacral eschar at admission to the DIFFICULT-TO-WEAN UNIT, by measurement of resting energy expenditure by calorimetry at admission to the DIFFICULT-TO-WEAN UNIT and by measurement of lean mass, fat mass and dilution by impedancemetry at admission to the Difficult-to-Wean Unit.

5 Patient selection

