3.2 Secondary objectives

The secondary objectives are to evaluate in tracheostomized patients hospitalized in Difficultto-Wean Unit:

- The prevalence of successful decanulation ;
- The prevalence of successful weaning from invasive ventilation;
- Factors associated with successful weaning from invasive ventilation (VI);
- Demographic characteristics of these patients at admission;
- The ventilatory characteristics of these patients at admission;
- Biological characteristics of these patients at admission;
- The nutritional status of these patients at admission.

4 Outcome

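### The factor list reused for the weaning objective contains one item that is essentially the weaning outcome and two that arise only after it

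*Combined protocol and SAP*

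**What the plan says.** Section 3.2 makes this a declared secondary objective: "Factors associated with successful weaning from invasive ventilation (VI". The candidates come from section 4.2: "The same factors potentially associated with successful weaning from IV will be collected as described in section 4.1". The same section defines the outcome: "Successful weaning from invasive ventilation is defined as the absence of invasive ventilation >48h". It gives no time point at which this is judged.

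The list in 4.1 has 21 items. Three matter most here:
- "Time to 24-hour at Difficult-to-Wean Unit de-ventilation (days"
- "Time from 24-hour deventilation to successful DIFFICULT-TO-WEAN UNIT decanulation (days"
- "Bronchial fibroscopy abnormalities prior to decanulation"

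Section 7.7 fixes when the first of these is recorded: "Complete 24-hour de-ventilation is recorded when the patient is de-ventilated for 48 hours without the need for re-ventilation". It then sets the order of the pathway: "Patient is deventilated 24 hours a day: the next step consists of placing a plug over the tracheostomy orifice". A period of 48 hours with the cannula plugged follows, then the assessments, and the fibroscopy is described last, before the cannula is removed.

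Section 10.3 describes a model only for success or failure of decanulation. Section 10.2 says in general terms that multivariable analyses will use linear or logistic regression. Neither says how a never-weaned patient is to be coded on the three factors.

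**The concern.** The list was written for decanulation. In that setting the time to 24-hour de-ventilation is an earlier step on the way to the outcome. When the outcome changes to weaning, the same variable becomes the time of the outcome, and two further items fall after it. A factor that exists only once the outcome has occurred cannot explain that outcome.

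At stake is the answer to a declared secondary objective. If the list is used as written, some comparisons have no values in the failure group. If values are supplied for failures by convention, the resulting association reflects the convention and says nothing about patients.

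**Working it through.** **The plan's own figure.** Section 10.1 uses 6 variables, 10 events per variable and 60% expected decanulation: 6 × 10 / 0.60 = 100. This reproduces the stated 100 patients. No corresponding figure is given for weaning.

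**Definitions side by side.**

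| | Event | Source |
|---|---|---|
| Weaning success | more than 48 h without invasive ventilation | 4.2 |
| Complete 24-hour de-ventilation | recorded after 48 h without re-ventilation | 7.7 |

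Apart from the boundary (more than 48 h against 48 h) and any later return to ventilation, these are the same event. The listed factor is the time at which it happens.

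**Order of events in 7.7.** Full de-ventilation, then plugging, then 48 h plugged, then assessments and fibroscopy, then removal of the cannula. The interval to decanulation starts at the weaning event. The fibroscopy comes after it.

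**Count of the 4.1 list.**

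| Group | Listed | Fixed at or before unit admission |
|---|---|---|
| Severity (ICU stay) | 7 | 7 |
| Ventilatory | 7 | 3 |
| Respiratory | 3 | 2 |
| Extra-respiratory | 4 | 3 |
| Total | 21 | 15 |

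The six that are not fixed at admission are the three factors above (21 − 3 = 18 left without them), time to first de-ventilation attempt, VAPs in the unit, and the swallowing score (18 − 3 = 15). The swallowing score is counted here because 7.5 places the assessment once several hours of de-ventilation a day are tolerated, although 9.2.2 and 9.5 list it at inclusion.

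**Effect on the comparison.** The documents give no weaning rate, so a range is assumed. Failures = 100 × (1 − rate).

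| Assumed weaning rate | Failures in 100 | Failures with a time to 24-hour de-ventilation |
|---|---|---|
| 60% | 40 | 0 |
| 70% | 30 | 0 |
| 80% | 20 | 0 |
| 90% | 10 | 0 |

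The last column treats every failure as a patient never off the ventilator for 48 h. A complete-case model containing this variable would then keep no failures and could not be fitted.

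Suppose instead that every failure is given a common end-of-stay value of 30 days (assumed; 6.3 gives an average stay of 1 month) and weaned patients have times between 3 and 29 days. A simulation with no true predictor gave an AUC of 1.0 at all four rates. That follows from the coding alone. With individual discharge days, some failures could leave before some slow successes are weaned, so separation need not be complete. The variable would still be an event time in one group and an end-of-stay time in the other.

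**Separate point: size of the smaller group.** In 7.7 weaning precedes decanulation, so 60 expected decanulations imply at least about 60 weaned patients and at most about 100 − 60 = 40 failures. Counting the smaller group at 10 per variable allows 40 / 10 = 4 variables at that ceiling, and 3, 2 or 1 at assumed weaning rates of 70%, 80% or 90%.

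**The case against.** The strongest reply is that no circular model is specified. Section 4.2 says that the factors will be collected; it does not say that they enter a regression, and 10.3 covers decanulation only. This stands. A reader might infer from 3.2 and 10.2 that the plan prescribes a circular weaning regression, but the text does not go that far. What it does prescribe is the candidate list, which is the only specification this objective has.

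A reader might also infer that the de-ventilation time has a value if and only if the patient is weaned. The documents do not support this: with no assessment time, a patient re-ventilated later could have a recorded time and still count as a failure.

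Nor is complete separation bound to occur. It requires a coding for failures that the plan does not state. If the p < 0.20 screen of 10.3 were reused, a variable with no values among failures could not be tested and so would not be selected. That avoids the bad fit but leaves an ad hoc decision where a stated list should be.

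On fibroscopy, 7.6 says only that it is routine before decanulation, and its place after weaning is inferred from the order in 7.7. Section 9.3 records at discharge whether it was done, which can be completed for everyone. The listed factor, however, is the abnormalities found, and those need an examination.

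A VAP in the unit may delay weaning as well as result from longer ventilation, so leaving it out is partly a modelling preference. Finally, a limit of two or three variables might be read as the plan's own rule. It is not: 10.1 counts successes as events, which at 60 to 90 weaned patients would allow 6 to 9. Counting the smaller group is a reviewer's standard.

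**Conclusion.** The point holds for the candidate list. Three of the 21 factors are unsuitable for the weaning outcome: one is essentially the time of that outcome and two arise after it. Never-weaned patients would generally have no value on them. Three more arise after admission and need the same care. Fifteen are usable unchanged, so the objective can be rescued.

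The conclusion rests on the near-identity of the 4.2 and 7.7 definitions and on the order of steps in 7.7. It does not depend on the assumed weaning rates or on the simulation, which only illustrate the effect. The ceiling of about 40 failures assumes that the 60% in 10.1 applies to all 100 included patients and that every decanulated patient counts as weaned. The matter affects a secondary objective and should be corrected before analysis.

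**What to change.** In 4.2, replace the cross-reference with a separate candidate list for weaning, limited to the 15 factors fixed at or before unit admission:
- the seven ICU-stay severity factors;
- failed extubations, duration of ventilation before tracheostomy, and type of tracheostomy;
- the admission lung ultrasound score and diaphragm assessment;
- confusional state, oral status and MRC score at admission.

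The three outcome-dependent factors then leave the list, as do time to first de-ventilation attempt, VAPs in the unit and the swallowing score. All six may be reported descriptively.

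Also in 4.2, state the time point at which weaning success is assessed and how a patient re-ventilated after it is classified. In section 10, add a short description of the weaning analysis and set its number of variables with the smaller weaning group in mind.

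The cost is a few lines of text. No new data are needed, and the sample size and patient care do not change.
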